| 2 | 0 mg | 50-mg cap | 50 mg |
| 3 | 25-mg cap | 50-mg cap | 75 mg |
| 4 | 50-mg cap | 50-mg cap | 100 mg |
| 5 | 50-mg cap | 100-mg cap | 150 mg |
| 6-12 | 100-mg cap | 100-mg cap | 200 mg |

At the end of treatment, a research coordinator will conduct a repeat research assessment. Measurement of serum %dCDT will be used to assess the validity of self-reported drinking. To facilitate intent-to-treat (ITT) analyses, all patients will be asked to complete all scheduled assessments and an end-of-treatment evaluation, for which they will be paid \$50. Patients will also be compensated \$50 for each of two post-treatment follow-up visits. Patients will receive \$10/visit for transportation costs for each visit after the screening visit (i.e., \$120 for all 12 visits, including post-treatment follow-up visits). They will also be paid \$5 for each visit at which they return the medication container (n=8 visits). The total compensation available to patients will be \$310 for full participation.

D.4. Study Treatments: Throughout the study, we will maintain double-blind conditions regarding medication condition. MM will be delivered by a nurse experienced in its use during a TOP trial. The physician will meet with the patient at the beginning of treatment (and as needed thereafter) and will meet with the nurse weekly to discuss clinical management. The nurse practitioner or study physician will order and dispense study medications.

D.4.a. Medication Condition: The maximal dosage of TOP to be used in the present study is 200 mg/day in two divided doses and a six-week titration period based on prior evidence of efficacy and tolerability (7,8). The nurse, in consultation with the study physician, will guide patients as they increase their medication dosage. TOP will be purchased commercially and formulated in opaque capsules by the Investigational Drug Service (IDS). Placebo capsules will be formulated to match the active medication.

D.4.b. Counseling. At each treatment visit, all patients will receive brief counseling using Medical Management (MM), a medically oriented intervention developed for the COMBINE Study (45). It supports the use of pharmacotherapy and maximizes medication adherence in the treatment of AUD. MM is feasible in most medical settings, but unlikely to obscure a medication effect. We modified the MM manual to include a goal of sensible drinking for use in our completed TOP study, where it was well received (7). In MM, the clinician highlights the patient's symptoms of AUD and his or her need for treatment, advising the patient to reduce or stop drinking (consistent with his/her goal), providing a rationale to take the medication, and emphasizing the importance of daily medication adherence. For patients who choose a goal of reduced drinking, we will use empirically based guidelines for non-hazardous drinking (49). These call for men to consume no more than 3 standard drinks per day and 12 standard drinks per week and women to consume no more than 2 drinks per day and 8 drinks per week. Thus, patients will be counseled both to avoid heavy drinking days and to increase the number of abstinent days.

Patients will receive MM at each treatment visit. The first MM session will last 30 minutes and subsequent sessions 20 minutes. At each session, the nurse checks the patient's BAL, vital signs, weight, adverse effects, medication adherence, and concurrent medications; performs a brief assessment of the patient's drinking and general functioning; and makes recommendations for the patient to follow until the next visit. Patients with severe psychological symptoms (e.g., suicidal thoughts judged by a study physician to be clinically significant) will be withdrawn from treatment and referred for care.

D.4.b.1. Ensuring Adherence to MM Content and Procedures: [name], the lead nurse practitioner, has more than 10 years of experience with MM, including in our completed TOP trial. She will train the nurses in the administration of MM by reviewing the protocol and manual with them, conducting role-playing and practice sessions, and reviewing audiotaped practice sessions until the nurses achieve adequate performance. [name] will also listen to 10% of recorded visits, evaluate the nurse practitioners' adherence to MM principles, record the total session time, assess the therapeutic relationship, and review the achievement of reduced drinking goals and clinical improvement during treatment. She will provide individual feedback to nurses (as needed) in monthly meetings to assure protocol adherence. Audiotapes will be destroyed after review. Her time will be contributed by the VISN 4 MIRECC.

D.5. Assessments: We include measures from different sources (see Table 2 below) to cover the various domains in which alcohol treatment may exert an effect and to corroborate treatment effects.

D.5.a. Laboratory/Medical Assessments: These assessments serve: 1) to screen patients for medical exclusion criteria, 2) to assess potential adverse effects of TOP, and 3) to corroborate self-reported drinking. Prior to entrance into the study, each patient will receive a physical examination, urinalysis and urine toxicology, complete blood count (CBC), a chemistry panel [which includes electrolytes, liver enzymes (ASAT, ALAT, %dCDT), bilirubin, uric acid, blood urea nitrogen (BUN), and creatinine], and pregnancy testing. Pregnancy testing will be repeated monthly. If at screening, a patient is found to be pregnant, she will be excluded from participation and referred for obstetric evaluation. If the patient is found to be pregnant at one of

the follow-up tests, she will immediately be withdrawn from treatment with medication, referred for obstetric evaluation, and advised to discontinue all drinking. At the midpoint and end of the 12-week treatment phase, %dCDT will be repeated to corroborate self-reported alcohol consumption.

D.5.b. Psychological/Behavioral Assessments: Although TOP is hypothesized to have its greatest influence on heavy drinking, other assessments are included to evaluate improvement in multiple domains.

D.5.b.1. Areas assessed only at intake:

a. Enrollment Logs and Patient Tracking: Procedures designed to maintain confidentiality include both formal training sessions for all RAs in the importance of procedures to be followed, as well as formal mechanisms for limiting access to all information that can link data to individual patients. Data forms do not include identifying information. To facilitate tracking, the PI will maintain, under a limited password, a computer file with the identity of patients, their ID numbers and information about how they can be reached. However, this file will contain no clinical data. At the time of initial contact, the RA will assign each patient a unique ID number, which will serve to represent patients during data entry and file management procedures.

b. Sociodemographic/general patient information: During screening, an assessment of medical history, personal and family history of alcoholism, marital status, educational and occupational information and substance abuse treatment history will be obtained using questionnaires and interviews described below.

c. Locator information: At the time of enrollment in the study, the RA will select patient locators on the basis of their relationship to the patient, duration and current status of the relationship, frequency of contact with the patient, and willingness to participate. Locators are contacted when efforts to reach a patient are unsuccessful, which enhances retention of patients in treatment and for purposes of data collection.

d. Psychiatric diagnosis: The Structured Clinical Interview for DSM-5 (SCID) will be used to classify patients according to the presence or absence of standard psychiatric disorders according to DSM-5 criteria.

e. Family history of alcohol dependence: The Family History Assessment Module systematically queries the patient about the presence of an alcohol use disorder (AUD) in relatives. The patient will provide information concerning parents' and siblings' history of AUD criteria without their being identified. We will examine family history in relation to any of the candidate variants as part of validating these as pharmacogenetic moderators.

D.5.b.2. Areas assessed only at treatment endpoint:

a. Overall condition at the end of treatment (for early withdrawal from the study): The Early Termination Form, indicating the patient's level of functioning at termination, will be completed by the nurse for any patients that leave treatment prematurely. The form is used to identify the reasons for early termination (e.g., non-response, adverse effects) and other relevant circumstances. Patients unable to return for the endpoint will be mailed all questionnaires (with a stamped envelope for ease of return) and then interviewed by telephone. Patients will be compensated to complete the assessments. Using this and similar methods, we have been successful in obtaining 90% of data from subjects in alcohol treatment trials.

D.5.b.3. Areas assessed at intake and end of treatment:

a. Alcohol use patterns: The Timeline Follow-back (TLFB) (50) will be used to estimate past 90-day drinking at intake and at every treatment visit going back in time from the last assessment. The TLFB is reliable and valid when used by trained interviewers.

b. Alcohol-related problems: The Short Index of Problems (SIP), a 15-item instrument, was derived from the 50-item DrInC (32) and measures a single factor of alcohol-related problems (51). It proved to be sensitive as a measure of treatment outcome in our completed trial of TOP (7). As in that study, SIP scores will be used to describe the pretreatment alcohol-related problem severity of the sample and for concurrent validation of self-reported drinking during treatment and follow-up.

D.5.b.4. Areas assessed at each visit

a. Medication usage: The primary measure of medication adherence is recording of the pills dispensed and those taken by the patient from blister cards. The blister cards are prepared by the research pharmacist to be given as weekly packets. Blister cards have several advantages over pill counts, MEMS caps or riboflavin, including low cost, direct feedback to the patient regarding adherence, and ease of delivery (52). The use of riboflavin has been particularly questioned as a measure on adherence (53). Patients will be asked to return the unused portion of study medication at each visit. They will be compensated \$5 for each visit at which they return the medication container.

b. Medication adverse effects: Patients will provide subjective reports of side effects at each study visit using the Systematic Assessment for Treatment Emergent Effects (SAFTEE) interview, a widely used measure that has been standardized for use in alcohol treatment trials (54).

c. Psychological symptoms: 1) The Patient Health Questionnaire (PHQ-9), a 9-item self-report measure of depressive symptoms with a total score of 0-27, will be completed at each visit (55). This is useful both to characterize the sample for comparison with other study samples and for monitoring patients' safety.

d. Measures of treatment received: We will keep records of medication taken and additional treatment received, including individual and group substance abuse and psychiatric treatment and self-help group participation.

| Table 2: Schedule of Assessments | | | | | | |
|---|-----------|--------------|------------------------------|----------|--|----------------|
| Instrument | Rater | Patient Time | Screen | Baseline | Weekly/Monthly | Endpt & F/U's |
| Review of Criteria & Informed Consent | CL | 20 min | X | | | |
| Medical History & Physical Exam | CL | 20 | | X | | |
| Laboratory Tests (blood for DNA only at screening; urine for urinalysis and urine toxicology only at screening) | Lab | 5 | Chem. panel, CBC, U/A, %dCDT | | Midpoint: bicarb, %dCDT; Monthly: preg. test | %dCDT |
| Demographic Interview | RC | 10 | X | | | |
| Locator Information | RC | 2 | X | | | |
| Structured Clinical Interview for DSM-5 | RC | 30 | X | | | X ^b |
| Family History Assessment Method | RC | 10 | X | | | |
| Timeline Follow-Back Interview | RC | 20 | X | | X ^a | X |
| Short Index of Problems | P | 15 | | X | | X |
| Patient's Health Questionnaire-9 | P | 3 | | X | X | X |
| Medication Usage | RC | 3 | | | X | X |
| Systematic Assessment for Treatment Emergent Effects | P, CL | 5 | | X | X | X |
| Measures of Treatment Received | P, CL, RC | 5 | | X | X | X |
| Other Medical Management Procedures | P, CL | 10 | | | X | X ^c |
| Early Termination Form | CL | 10 | | | | X ^d |

CL = Clinician (Nurse Practitioner or Physician); RC = Research Coordinator; P = Patient ; F/U = follow-up visits at 3- and 6 months post-treatment

^aTimeline Follow-back data will be collected at each visit to cover the period since the last visit.

^bAUD diagnosis only at Endpoint and Follow-up visits

^cOnly at Endpoint

^dOnly for patients who do not complete the 12-week treatment

D.5.c. Design and Methodological Considerations

D.5.c.1. We chose a 12-week treatment period to ensure that patients receive adequate exposure to TOP at a dosage adequate to produce a treatment effect. We will focus the analysis on the last six weeks of treatment, by which time the TOP dosage will be 200 mg/day, a dosage at which clear separation from placebo has been seen in prior studies (5-8).

D.5.c.2. We chose the 200-mg/day dosage of TOP, which was shown by Miranda et al. (8) and by us (7) to be well tolerated and to reduce heavy drinking significantly. The 300-mg dosage, although efficacious, resulted in significantly greater dropout than placebo in a multi-center trial (6).

D.5.c.3. We chose to use the immediate-release formulation of TOP, administered twice daily, rather than Trokendi XR™ or Quedxy XR™, which are new, once-daily formulations of TOP. We chose the immediate-release formulation of TOP because it is generic and inexpensive, and its use to treat AUD in the VAHS is growing rapidly (9). If TOP is efficacious in this study, it would be of potential interest to compare the efficacy and tolerability of the immediate-release and the once-daily TOP formulations, which is beyond the scope of the present proposal.

D.5.c.4. We will enroll actively drinking individuals with a goal of reduced drinking or abstinence because studies using these goals showed robust effects of TOP in reducing heavy drinking. Although we will include patients with a DSM-5 diagnosis of AUD, we will require that patients have a weekly average of ≥ 2 heavy drinking days during the month before screening, consistent with the inclusion criteria for our TOP study in heavy drinkers (7). These criteria will enhance the study's external validity and applicability to the current diagnostic system while ensuring that we can detect a treatment effect on heavy drinking days.

D.5.c.5. We propose to use the MVP data to identify candidates for evaluation as moderators of the TOP response in AAs because it provides a large sample of Veterans whose demographics and other features would be most like the sample that we are recruiting for the proposed trial. Although [name] is one of the principal investigators on a beta project analyzing the GWAS data from the MVP for the phenotype of sustained heavy drinking, it may not be feasible to access the data for the purpose of the analyses proposed here. As a backup for that exploratory analysis, we will use data from our GWAS in AAs to which we have already have full access (11).

D.5.d. Rater reliability: We will aim to have the same rater interview each patient throughout the study, at the same time of day, to enhance the reliability of research ratings. We will conduct standardized rater training at the outset and ongoing quarterly assessments of performance to reduce "drift."

D.6. Genotyping: Data for this aim will come from a genomewide association study (GWAS) being conducted by the Million Veteran Program (MVP) or, alternatively, from GWAS data that we obtained in a sample of 3,318 AAs (11). We will collect a sample of whole blood to use for genotyping patients for the SNPs that are identified through beta testing of the MVP dataset as potential moderators of TOP response.

D.7. Data Analyses: The study will use the web-based direct entry data management system of the Penn Center for Studies of Addiction, with data stored on secure servers at the CMCVAMC. This arrangement has been approved and is described in a Memorandum of Understanding between the CMCVAMC and the Perelman School of Medicine at Penn. Interview data and self-report data are entered directly onto computers by research staff and/or subjects under supervision by staff. A range of checks for the validity of responses (including field validation to ensure that no out-of-range or otherwise invalid responses are accepted), and form validation (to ensure that logically impossible responses to different questions are not accepted) are built into this entry process. After entry, the research staff performs a brief review to ensure that the form has been completed. On completion of this review, the technician transmits the data (in 128-bit encrypted form) over the Internet to the DMU data servers. After a series of online reviews, the data are archived on the servers without protected health information. Audit logs record any modification to the original entry. Various levels of password protection will allow access to the data by members of the research team.

An important initial consideration will be to identify baseline differences between groups that may have occurred despite the use of block randomization. Prior to analysis, the distribution of outcome data will also be examined to determine the need for transformation and whether parametric analytic methods can be used.

D.7.a. To examine the effects of TOP treatment on the number of heavy drinking and abstinent days during the final six weeks of treatment (Specific Aim 1). The two primary outcomes, which will be measured using the TLFB, are the frequency of heavy drinking days (≥ 5 standard drinks in a day for men and ≥ 4 in a day for women), a sensitive, clinically relevant measure in alcohol treatment trials, and the frequency of abstinent days (56). An attempt will be made to evaluate outcomes for all patients irrespective of whether they continue to receive treatment, so that the analysis of all outcomes will be based on all of the data available for all randomized patients. Secondary outcomes for Aim 1 will include the severity of alcohol-related problems (i.e., SIP score) and %dCDT, which will be analyzed using models similar to those described below for the primary outcomes.

The two medication groups will be compared on weekly number of heavy drinking days and weekly number of abstinent days using mixed effects models for count responses, fitted using PROC GLIMMIX in SAS and the HGLM module of the HLM7 program (57). Estimates of effects over the final six weeks from the models, with associated standard errors and confidence intervals, will be used to test the primary hypotheses, i.e., that TOP treatment will reduce heavy drinking days and increase abstinent days more than placebo during the final six weeks of treatment. The models will include covariates for linear and quadratic time trends, as appropriate for model fit. The random effects will include a random intercept and, if necessary, residual autocorrelations, random slopes, or other specifications will be used. Although the primary contrasts will concentrate on the final six weeks, these models utilize all available data from all patients, so the analyses follow the intent-to-treat principle.

D.7.b. To explore the moderating effects of variation at *GRIK1* and other glutamate system genes on the efficacy of TOP 200 mg/day in reducing the frequency of heavy drinking and increasing the frequency of abstinent days (Specific Aim 2). Specific Aim 2 will be addressed by including a binary indicator of the SNPs identified as being associated to sustained heavy drinking through the MVP beta test project in the models described above for testing Specific Aims 1. These models will include the main effect of the SNP indicator and its interaction with medication group and time. Analyses will be conducted and results described as above. To identify candidate variants to test in the pharmacogenetic analyses, we will select SNPs in *GRIK1* and *GRIK2* (the genes that encode the GluK1 and GluK2 kainate subunits, on which TOP's effects are most potent and selective (39), using data from the MVP project, or alternatively from the GWAS that we completed on 3,318 AAs (11). We will select the 10 SNPs in these genes that yield the smallest p-values (ideally, but not necessarily, the p-values for these SNPs will be smaller than the p-value that is typically used to determine genomewide significance: $p < 5.0 \times 10^{-8}$). We will test for moderating effects by starting with the most significant SNP and continuing until one shows significance, with the value of α adjusted each time to reflect the number of comparisons (such that the tenth SNP would be tested using $\alpha = 0.005$). We will also construct a gene-based analysis, considering common variation mapped to genes that are implicated as being associated to sustained heavy drinking in the MVP sample or alcohol dependence in our sample (11). We will use the approach developed by Lin and et al. (58), where the interaction effect between an environment (treatment in our case) and all the SNPs within a gene can be considered in a unified framework. Analyses will be conducted and results described, as above. In particular, separate estimates and confidence intervals will be reported for the TOP effects in the two levels of each binary genotypic indicator. The outcomes for Aim 2 are exploratory.

D.7.c. To examine the persistence of effects of TOP treatment on the number of heavy drinking and abstinent days during a six-month post-treatment follow-up period (Specific Aim 3). We will use linear mixed models to examine medication group differences in percent heavy drinking days, percent days abstinent, SIP, GGTP, and %dCDT across the treatment and post-treatment periods. The 12-week treatment period, along with the 3-month and 6-month follow-up periods will be included in the analysis to determine whether the change in outcomes from treatment to follow-up differ by medication group. The models will include study period (treatment period, 3-month follow-up, 6-month follow-up), treatment group (TOP, placebo) and the interaction between these two factors to test for differences between study periods, treatment groups, and the change in the difference between groups across study periods. Baseline (pretreatment) values for each outcome will be included as covariates in modeling the respective outcome. The outcomes for Aim 3 are considered exploratory. We will also explore the persistence of TOP effects using the primary SNP identified in Aim 2. That is, we will conduct a pharmacogenetic analysis of the persistent effects of TOP, similar to our analysis of heavy drinking in EAs, where rs2832407*C homozygotes treated with TOP had robust reductions in heavy drinking during the six-month post-treatment period (10).

D.7.d. Dropout and Missing Data: We will base the primary relative efficacy comparisons in the trial on mixed effects models utilizing all data provided by participants. In our completed TOP trial, we saw limited dropout (8% to the start of the final six weeks, and 4% thereafter). We will assess the sensitivity of our assumption that missing data are ignorable by running models that address missingness in different ways. For mixed effects models, pattern mixture models test for differences in regression estimates across patterns of missing data, and shared parameter models allow for correlated random effects for the primary responses and the week-to-week binary indicators of missing/complete data (57). Semi-parametric regression models use inverse probability weighting to extend the validity of GEE models, and provide a different type of sensitivity analysis for the mixed effects models (59). All of these modeling approaches require certain model assumptions, so we will compare the results of the analyses over a range of such assumptions.

D.7.e. Adherence: To assess the sensitivity of the results of the analyses described above to non-adherence, the models described above for our primary and secondary outcomes will be extended using instrumental variable approaches. Under some assumptions, these analyses will yield estimates of the intervention effects that would have been seen in a study with full adherence. To analyze data using a single overall measure of adherence (e.g., 80% of assigned medication taken over the 12 weeks of treatment), we will use the methods of Nagelkerke et al. (60). We will also examine longitudinal extensions of these methods, looking at weekly adherence to medications as a time varying measure (61).

D.7.f. Adequacy of Sample Size for Specific Aim 1: The analyses described above make use of all data provided by all patients to estimate models from which contrasts restricted to the final six weeks will test the TOP effect on days of heavy drinking and abstinent days (Specific Aim 1). Power for the contrasts will be determined by the patterns of outcomes in the final six weeks, so power estimates are based on weeks 7

through 12 as a 6-week trial, with adjustments for loss to attrition between baseline and week 6. Based on our prior study (7) we anticipate 92% retention through the first six weeks for each group, yielding 74 available per group at the end of week 6, an additional 4% loss due to dropout across the final six weeks, and a within-subject correlation of about 0.6. The methods of Hedeker et al show that we will have 80% power for a TOP main effect size of $d=0.40$, 0.43 , and 0.46 , for within-subject correlations of 0.5 , 0.6 , and 0.7 , respectively, at a corrected alpha level of 0.025 (62). In [name] et al, the effect sizes for heavy drinking days in weeks 7 through 12 varied between $d=0.52$ and $d=0.62$, so the sample size should be adequate to detect similar effects in the current study (7).

D.7.g. Adequacy of Sample Size for Specific Aims 2 and 3: The analyses to address these aims are based on the expectation that genetic variation will be identified that moderates the response to TOP in AAs, in a manner analogous to that seen in EAs, in which the most robust post-treatment effects were observed in individuals with a specific TOP-responsive genotype (10). We acknowledge that the sample may not be large enough to provide adequate power for definitive analyses for these Aims. However, we believe that the knowledge gained, including estimates of effect sizes of moderator effects (**Specific Aim 2**) and persistent effects (**Specific Aim 3**), will inform subsequent TOP studies in AAs with AUD.

D.7.h. Safety: Safety will be analyzed using categorical outcomes, defined by the type and severity of adverse effects. Summary measures of adverse events will be developed by organ system from the SAFETEE and will be compared for patients receiving TOP or placebo using chi-square analysis.

Table 3: Timeline of Performance Goals

| Activity | Year 1 | Year 2 | Year 3 | Year 4 | Year 5 |
|-------------------------------------|--------|--------|--------|--------|--------|
| Staff training and study initiation | | | | | |
| Patient enrollment | | | | | |
| Endpoint assessments | | | | | |
| Follow-up Assessments | | | | | |
| Data cleaning | | | | | |
| Data analysis | | | | | |
| Report writing | | | | | |

REFERENCES

1. Caetano R. Alcohol-related health disparities and treatment-related epidemiological findings among whites, blacks, and Hispanics in the United States. *Alcoholism, clinical and experimental research*. 2003;27(8):1337-9. doi: 10.1097/01.ALC.0000080342.05229.86. PubMed PMID: 12966334.
3. Ray LA, [name] DW. Naltrexone for the treatment of alcohol dependence among African Americans: results from the COMBINE Study. *Drug and alcohol dependence*. 2009;105(3):256-8. doi: 10.1016/j.drugalcdep.2009.07.006. PubMed PMID: 19717248; PubMed Central PMCID: PMC3409877.

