D.3.a. Visit 1 (Baseline assessment): At this first visit, patients will have the study procedures explained to them, be given an opportunity to ask questions and be asked to provide informed consent. They will be required to have a zero breathalyzer reading to ensure that they are capable of giving informed consent. Patients will have their reading ability evaluated with the Slosson Oral Reading Test (47). The physician or nurse practitioner will obtain a medical and psychiatric history and will administer the Clinical Institute Withdrawal Assessment for Alcohol-Revised (CIWA-Ar) (48). If the CIWA-Ar score exceeds 10, the patient will be offered ambulatory medical detoxification prior to randomization. Patients with alcohol withdrawal deemed too severe to treat on an ambulatory basis (e.g., CIWA-Ar score > 20 , presence of a history of severe or complicated withdrawal) will be referred for inpatient detoxification. Blood and urine samples will be taken for routine clinical laboratory evaluations (including GGTP), drug screening, pregnancy testing, and DNA extraction. If necessary, the baseline assessment can be conducted over several visits to complete all assessments.

D.3.c. Visits 2-11 (Treatment and End-of-Treatment Visits): Patients will receive the first counseling session and study medication immediately following the randomization visit (i.e., in visit 2). The dosage of TOP or matching placebo will be gradually increased over 6 weeks (Table 1). In the multicenter trial of TOP (6), TOP 300 mg/day was associated with greater attrition than placebo. In contrast, in our TOP trial (7), patients received a maximal daily dosage of 200 mg of TOP, which was efficacious and well tolerated (84.9% of patients completed the study, with Timeline Follow-back data available on an average of 92.4% of days). We will use the 200-mg maximal dosage here and a block randomization scheme to balance patient assignment on treatment goal (reduced drinking vs. abstinence).

During the 12-week treatment period, patients will return to the clinic weekly for 6 weeks and biweekly for 6 weeks (i.e., a total of 9 sessions). At each visit, we will measure their breath alcohol level (BAL), weight, and vital signs. They will complete questionnaires and receive MM counseling (see below).

| Table 1: Dosing Schedule for Topiramate | | | |
|---|------------|------------|------------------|
| Wk | AM Dose | PM Dose | Total Daily Dose |
| 1 | 0 mg | 25-mg cap | 25 mg |

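### Assignment is blocked to balance treatment goal, but the primary models contain no goal term; if goal predicts drinking, the tests are conservative and some precision is lost

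*Combined protocol and SAP*

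**What the plan says.** - **Design.** D.3.c (Visits 2-11) states that the trial will use "a block randomization scheme to balance patient assignment on treatment goal (reduced drinking vs. abstinence". Goal is the only balancing factor named. Block size and mechanics are not given.
- **Primary models.** D.7.a compares the medication groups on "weekly number of heavy drinking days and weekly number of abstinent days using mixed effects models for count responses". On covariates it says: "The models will include covariates for linear and quadratic time trends, as appropriate for model fit". On random effects: "The random effects will include a random intercept and, if necessary, residual autocorrelations, random slopes, or other specifications will be used". Goal is not mentioned.
- **Baseline check.** The introduction to D.7 plans to "identify baseline differences between groups that may have occurred despite the use of block randomization". It does not say what follows if a difference is found.
- **Other models.** Baseline covariates are named only for Aim 3 (D.7.c), as the pretreatment value of each outcome. Goal is absent there too.
- **Power.** D.7.f makes no allowance for goal.

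**The concern.** Balancing assignment within goal groups means that differences in drinking between those groups largely cancel out of the treatment comparison. A model without goal does not know this. It leaves those differences in the between-patient variance, so the model-based standard error is larger than the true sampling error of the treatment effect. The tests then run below their nominal level, the intervals are too wide, and the precision that the blocking makes available is not used.

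The baseline check in D.7 would not repair this. It looks for imbalance between arms, and goal is balanced by design.

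The effect depends on goal being prognostic. That is plausible for abstinent days, one of the two primary outcomes. It is less so for heavy drinking days: D.4.b says "Thus, patients will be counseled both to avoid heavy drinking days and to increase the number of abstinent days", and its daily limits for reduced drinking (3 drinks for men, 2 for women) already lie below the heavy-drinking thresholds of 5 and 4.

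**Working it through.** **1. The plan's power figure.** Inputs from D.7.f: 92% retention to week 6, a further 4% loss, within-subject correlation 0.6, alpha 0.025, d = 0.43. Equal allocation of the 160 patients (implied by 74 per group) and two-sided tests are assumed.

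- Patients per group: 80 × 0.92 × 0.96 = 70.7, about 71.
- SD of a six-week mean, in units of the weekly SD: √((1 + 5 × 0.6)/6) = 0.816.
- Standard error: 0.816 × √(2/71) = 0.137.
- Power: Φ(0.43/0.137 − 2.241) = Φ(0.897) = 81.5%, against the stated 80%.

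The plan's figure is reproduced to within 2 points. Below, the noncentrality is set to give exactly 80% at d = 0.43: 2.241 + 0.842 = 3.083, scaled by d/0.43 for other effects.

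**2. Effect of leaving goal out.** Let R² be the share of the variance of a patient's six-week mean explained by goal, and q = √(1 − R²). With balance within goal, the true standard error of the contrast is q times the one the unadjusted model reports. Hence:

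- actual alpha = 2(1 − Φ(2.241/q))
- interval width ratio = 1/q
- power without goal = Φ((ncp − 2.241)/q)
- power with goal = Φ(ncp/q − 2.241)

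R² is not in the documents and is assumed. If a share s chooses abstinence and the goal groups differ by δ within-goal SDs, then R² = s(1 − s)δ²/(1 + s(1 − s)δ²). For s = 0.3, δ = 0.5 this is 0.05; for s = 0.5, δ = 1 it is 0.20.

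| R² | Actual alpha | Interval width ratio | Power at d = 0.43, without / with goal | d = 0.52 | d = 0.62 |
|---|---|---|---|---|---|
| 0 | 0.025 | 1.000 | 80.0 / 80.0% | no change | no change |
| 0.05 | 0.0215 | 1.026 | 80.6 / 82.2% | 93.6 / 94.3% | 98.8 / 99.0% |
| 0.20 | 0.0122 | 1.118 | 82.7 / 88.6% | 95.2 / 97.3% | 99.3 / 99.7% |

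From unrounded values, the power forgone at R² of 5% to 20% is 1.6 to 5.9 points at d = 0.43, 0.7 to 2.1 at d = 0.52 and 0.2 to 0.4 at d = 0.62. D.7.f cites d = 0.52 to 0.62 for heavy drinking days in the earlier trial. It gives no expected d for abstinent days.

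**3. Check in a count mixed model.** The formula above is for linear models, so the level was also simulated with a Poisson random-intercept model fitted by maximum likelihood (Wald test at 0.025, no drug effect). Settings: 148 patients (2 × 74), correlation 0.6, six weekly counts; assumed mean 2.5 days a week, 40% with an abstinence goal, blocks of 4 within goal. There were 20,016 runs per row, with a Monte Carlo standard error of 0.0011.

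| Ratio of mean days between goal groups | Alpha without goal | Alpha with goal |
|---|---|---|
| 1.0 | 0.0263 | 0.0268 |
| 1.25 | 0.0246 | 0.0267 |
| 1.5 | 0.0209 | 0.0264 |
| 2.0 | 0.0137 | 0.0266 |

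The reported standard error without goal is 1.04 times the one with goal at a ratio of 1.5, and 1.11 times at 2.0. The direction and size agree with the formula. The loss is visible only from a ratio of about 1.5.

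**The case against.** The strongest reply is that the plan's conclusions are safe as written. There is no bias, the false-positive rate does not rise, and power without the goal term never falls below the planned 80%; it rises slightly as R² grows. At the effects expected for heavy drinking days the forgone power is about 2 points at most, on power already above 93%. The 5.9-point figure needs both the minimum detectable effect and goal groups a full SD apart. No figure in the documents shows that goal predicts drinking at all, and baseline drinking, if added as a covariate, might absorb part of what goal explains. All of this stands and limits the weight of the point.

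Three further objections carry less:

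- **Unbounded counts.** The Poisson simulation allows more than 7 days a week; at a ratio of 2.0 about 10% of weekly counts in the higher group would do so. A separate simulation capped at 7 days showed the same fall in alpha without goal, from about 0.028 to 0.014, and a roughly nominal level with it.
- **Which variance R² refers to.** At correlation 0.6, between-patient variance is 0.6/0.667 = 90% of the variance of the six-week mean. Goal explaining 5% or 20% of between-patient variance therefore means R² of 4.5% or 18%: alpha 0.0218 or 0.0133, and at most 5.4 points of power forgone at d = 0.43. The change is slight.
- **D.7.a is a summary.** It excludes no covariate, and blocking within goal groups is inferred. But the plan names baseline covariates where it wants them, in Aim 3, and a covariate left unnamed is not prespecified.

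**Conclusion.** The concern holds. The trial balances assignment on goal, and no analysis model uses it. To the extent that goal predicts drinking, the primary tests are conservative and their intervals too wide: actual level 0.022 to 0.012 and intervals 3% to 12% too wide for R² of 5% to 20%. If goal is not prognostic, the cost is nil.

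This is a loss of efficiency and does not threaten validity. It matters most for abstinent days, where goal is most likely to be prognostic and the plan gives no expected effect to show a margin above d = 0.43. The result rests on 1:1 allocation, two-sided tests, blocking within goal groups, and assumed values for the goal split and goal effect.

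**What to change.** In D.7.a, state that treatment goal as randomised (reduced drinking or abstinence) enters both primary models as a fixed effect, and carry it into the missing-data sensitivity versions in D.7.d. Adding it to the secondary models and to the exploratory Aim 2 and Aim 3 models is optional, for consistency.

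The cost is one sentence and one degree of freedom. Goal must already be recorded in order to randomise, so no new data are needed and the sample size does not change.
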